5.3.5.6 Abnormal Liver Function Tests

The finding of an elevated ALT or AST ($> 3 \times \text{ULN}$) in combination with either an elevated total bilirubin ($> 2 \times \text{ULN}$) or clinical jaundice in the absence of cholestasis or other causes of hyperbilirubinemia is considered to be an indicator of severe liver injury (as defined by Hy's law). Therefore, investigators must report as an adverse event the occurrence of either of the following:

- Treatment-emergent ALT or AST $> 3 \times \text{ULN}$ in combination with total bilirubin $> 2 \times \text{ULN}$
- Treatment-emergent ALT or AST $> 3 \times \text{ULN}$ in combination with clinical jaundice

The most appropriate diagnosis or (if a diagnosis cannot be established) the abnormal laboratory values should be recorded on the Adverse Event eCRF (see Section 5.3.5.1) and reported to the Sponsor immediately (i.e., no more than 24 hours after learning of the event), either as a serious adverse event or an adverse event of special interest (see Section 5.4.2).

5.3.5.7 Deaths

For this protocol, mortality is an efficacy endpoint. Deaths that occur during the protocol-specified adverse event reporting period (see Section 5.3.1) that are attributed by the investigator solely to progression of underlying disease should be recorded only on the Study Discontinuation eCRF. All other on-study deaths, regardless of relationship to study drug, must be recorded on the Adverse Event eCRF and immediately reported to the Sponsor (see Section 5.4.2).

Death should be considered an outcome and not a distinct event. The event or condition that caused or contributed to the fatal outcome should be recorded as the single medical concept on the Adverse Event eCRF. Generally, only one such event should be reported. If the cause of death is unknown and cannot be ascertained at the time of reporting, "**unexplained death**" should be recorded on the Adverse Event eCRF. If the cause of death later becomes available (e.g., after autopsy), "unexplained death" should be replaced by the established cause of death. *The term "sudden death" should not be used unless combined with the presumed cause of death (e.g., "sudden cardiac death").*

During survival follow-up, deaths attributed to progression of underlying disease should be recorded only on the Study Discontinuation eCRF.

5.3.5.8 Preexisting Medical Conditions

A preexisting medical condition is one that is present at the screening visit for this study. Such conditions should be recorded on the General Medical History and Baseline Conditions eCRF.

A preexisting medical condition should be recorded as an adverse event only if the frequency, severity, or character of the condition worsens during the study. When recording such events on the Adverse Event eCRF, it is important to convey the concept that the preexisting condition has changed by including applicable descriptors (e.g., "more frequent headaches").

5.3.5.9 Lack of Efficacy or Worsening of Cancer

Events that are clearly consistent with the expected pattern of disease evolution should not be recorded as adverse events. These data will be captured as efficacy assessment data only. In most cases, the expected pattern of progression will be based on mINRC, RANO criteria for HGG, RANO criteria for LGG, or RECIST v1.1, as appropriate. In rare cases, the determination of clinical progression will be based on symptomatic deterioration. However, every effort should be made to document progression through use of objective criteria. If there is any uncertainty as to whether an event is due to disease progression, it should be reported as an adverse event.

5.3.5.10 Hospitalization or Prolonged Hospitalization

Any adverse event that results in hospitalization (i.e., in-patient admission to a hospital) or prolonged hospitalization should be documented and reported as a serious adverse event (per the definition of serious adverse event in Section 5.2.2), except as outlined below.

An event that leads to hospitalization under the following circumstances should not be reported as an adverse event or a serious adverse event:

- Hospitalization for respite care
- Hospitalization for a preexisting condition, provided that all of the following criteria are met:
 - The hospitalization was planned prior to the study or was scheduled during the study when elective surgery became necessary because of the expected normal progression of underlying disease
 - The patient has not experienced an adverse event
- Hospitalization due solely to progression of underlying disease

An event that leads to hospitalization under the following circumstances is not considered to be a serious adverse event, but should be reported as an adverse event instead:

- Hospitalization for an adverse event that would ordinarily have been treated in an outpatient setting had an outpatient clinic been available

5.3.5.11 Adverse Events Associated with an Overdose or Error in Drug Administration

An overdose is the accidental or intentional use of a drug in an amount higher than the dose being studied. An overdose or incorrect administration of study treatment is not itself an adverse event, but it may result in an adverse event. All adverse events associated with an overdose or incorrect administration of study drug should be recorded on the Adverse Event eCRF. If the associated adverse event fulfills seriousness criteria, the event should be reported to the Sponsor immediately (i.e., no more than 24 hours after learning of the event; see Section 5.4.2).

No safety data related to overdosing of cobimetinib are available.

5.4 IMMEDIATE REPORTING REQUIREMENTS FROM INVESTIGATOR TO SPONSOR

Certain events require immediate reporting to allow the Sponsor to take appropriate measures to address potential new risks in a clinical trial. The investigator must report such events to the Sponsor immediately; under no circumstances should reporting take place more than 24 hours after the investigator learns of the event. The following is a list of events that the investigator must report to the Sponsor within 24 hours after learning of the event, regardless of relationship to study drug:

- Serious adverse events (see Section 5.4.2 for further details)
- Adverse events of special interest, regardless of seriousness (see Section 5.4.2 for further details)
- DLTs (immediate reporting during the DLT assessment window; see Section 5.4.2 for further details)
- Pregnancies (see Section 5.4.3 for further details)

The investigator must report new significant follow-up information for these events to the Sponsor immediately (i.e., no more than 24 hours after becoming aware of the information). New significant information includes the following:

- New signs or symptoms or a change in the diagnosis
- Significant new diagnostic test results
- Change in causality based on new information
- Change in the event's outcome, including recovery
- Additional narrative information on the clinical course of the event

Investigators must also comply with local requirements for reporting serious adverse events to the local health authority and IRB/EC.

5.4.2.1 Events That Occur prior to Study Drug Initiation

After informed consent has been obtained but prior to initiation of study drug, only serious adverse events caused by a protocol-mandated intervention should be reported. The Serious Adverse Event/Adverse Event of Special Interest Reporting Form provided to investigators should be completed and submitted to the Sponsor or its designee immediately (i.e., no more than 24 hours after learning of the event), either by faxing or by scanning and emailing the form using the fax number or email address provided to investigators.

5.4.2.2 Events That Occur after Study Drug Initiation

After initiation of study drug, serious adverse events and adverse events of special interest will be reported until 30 days after the last dose of study drug. DLTs will be reported during the DLT assessment window. Investigators should record all case details that can be gathered immediately (i.e., within 24 hours after learning of the event) on the Adverse Event eCRF and submit the report via the electronic data capture (EDC) system. A report will be generated and sent to Roche Safety Risk Management by the EDC system.

In the event that the EDC system is unavailable, the Serious Adverse Event/Adverse Event of Special Interest Reporting Form provided to investigators should be completed and submitted to the Sponsor or its designee immediately (i.e., no more than 24 hours after learning of the event), either by faxing or by scanning and emailing the form using the fax number or email address provided to investigators. Once the EDC system is available, all information will need to be entered and submitted via the EDC system.

Instructions for reporting post-study adverse events are provided in Section [5.6](#).

5.4.3 Reporting Requirements for Pregnancies

5.4.3.1 Pregnancies in Female Patients

Female patients of childbearing potential will be instructed to immediately inform the investigator if they become pregnant during the study or within 3 months after the last dose of study drug. The Clinical Trial Pregnancy Reporting Form provided to investigators should be completed and submitted to the Sponsor or its designee immediately (i.e., no more than 24 hours after learning of the pregnancy), either by faxing or by scanning and emailing the form using the fax number or email address provided to investigators. Pregnancy should not be recorded on the Adverse Event eCRF. The investigator should discontinue study drug and counsel the patient, discussing the risks of the pregnancy and the possible effects on the fetus. Monitoring of the patient should continue until conclusion of the pregnancy. Any serious adverse events associated with the pregnancy (e.g., an event in the fetus, an event in the mother during or after the pregnancy, or a congenital anomaly/birth defect in the child) should be reported on the Adverse Event eCRF. In addition, the investigator will submit a Clinical Trial Pregnancy Reporting Form when updated information on the course and outcome of the pregnancy becomes available.

5.4.3.2 Pregnancies in Female Partners of Male Patients

Male patients will be instructed through the Informed Consent Form to immediately inform the investigator if their partner becomes pregnant during the study or within 3 months after the last dose of study drug. The Clinical Trial Pregnancy Reporting Form provided to investigators should be completed and submitted to the Sponsor or its designee immediately (i.e., no more than 24 hours after learning of the pregnancy), either by faxing or by scanning and emailing the form using the fax number or email address provided to investigators. Attempts should be made to collect and report details of the course and outcome of any pregnancy in the partner of a male patient exposed to study drug. When permitted by the site, the pregnant partner would need to sign an Authorization for Use and Disclosure of Pregnancy Health Information to allow for follow-up on her pregnancy. If the authorization has been signed, the investigator should update the Clinical Trial Pregnancy Reporting Form with additional information on the course and outcome of the pregnancy. An investigator who is contacted by the male patient or his pregnant partner may provide information on the risks of the pregnancy and the possible effects on the fetus, to support an informed decision in cooperation with the treating physician and/or obstetrician. In addition, the investigator will submit a Clinical Trial Pregnancy Reporting Form when updated information on the course and outcome of the pregnancy becomes available.

5.4.3.3 Abortions

A spontaneous abortion should be classified as a serious adverse event (as the Sponsor considers abortions to be medically significant), recorded on the Adverse Event eCRF, and reported to the Sponsor immediately (i.e., no more than 24 hours after learning of the event; see Section [5.4.2](#)).

If a therapeutic or elective abortion was performed because of an underlying maternal or embryofetal toxicity, the toxicity should be classified as a serious adverse event, recorded on the Adverse Event eCRF, and reported to the Sponsor immediately (i.e., no more than 24 hours after learning of the event; see Section 5.4.2). A therapeutic or elective abortion performed for reasons other than an underlying maternal or embryofetal toxicity is not considered an adverse event.

All abortions should be reported as pregnancy outcomes on the paper Clinical Trial Pregnancy Reporting Form.

5.4.3.4 Congenital Anomalies/Birth Defects

Any congenital anomaly/birth defect in a child born to a female patient exposed to study drug or the female partner of a male patient exposed to study drug should be classified as a serious adverse event, recorded on the Adverse Event eCRF, and reported to the Sponsor immediately (i.e., no more than 24 hours after learning of the event; see Section 5.4.2).

5.5 FOLLOW-UP OF PATIENTS AFTER ADVERSE EVENTS

5.5.1 Investigator Follow-Up

The investigator should follow each adverse event until the event has resolved to baseline grade or better, the event is assessed as stable by the investigator, the patient is lost to follow-up, or the patient withdraws consent. Every effort should be made to follow all serious adverse events considered to be related to study drug or trial-related procedures until a final outcome can be reported.

During the study period, resolution of adverse events (with dates) should be documented on the Adverse Event eCRF and in the patient's medical record to facilitate source data verification.

All pregnancies reported during the study should be followed until pregnancy outcome. Follow reporting instructions provided in Section 5.4.3.1.

5.5.2 Sponsor Follow-Up

For serious adverse events, adverse events of special interest, and pregnancies, the Sponsor or a designee may follow up by telephone, fax, electronic mail, and/or a monitoring visit to obtain additional case details and outcome information (e.g., from hospital discharge summaries, consultant reports, autopsy reports) in order to perform an independent medical assessment of the reported case.

5.6 POST-STUDY ADVERSE EVENTS

The Sponsor should be notified if the investigator becomes aware of any serious adverse event that occurs after the end of the adverse event reporting period (defined as 30 days after the last dose of study drug), if the event is believed to be related to prior study drug treatment.

The investigator should report these events directly to the Sponsor or its designee, using the Adverse Event eCRF via the electronic data capture (EDC) system, unless EDC is no longer available; in which case, they should be faxing or by scanning and emailing the Serious Adverse Event/Adverse Event of Special Interest Reporting Form using the fax number or email address provided to investigators.

5.7 EXPEDITED REPORTING TO HEALTH AUTHORITIES, INVESTIGATORS, INSTITUTIONAL REVIEW BOARDS, AND ETHICS COMMITTEES

The Sponsor will promptly evaluate all serious adverse events and adverse events of special interest against cumulative product experience to identify and expeditiously communicate possible new safety findings to investigators, IRBs, ECs, and applicable health authorities based on applicable legislation.

To determine reporting requirements for single adverse event cases, the Sponsor will assess the expectedness of these events using the following reference document:

- Cobimetinib Investigator's Brochure

The Sponsor will compare the severity of each event and the cumulative event frequency reported for the study with the severity and frequency reported in the applicable reference document.

Reporting requirements will also be based on the investigator's assessment of causality and seriousness, with allowance for upgrading by the Sponsor as needed.

6. STATISTICAL CONSIDERATIONS AND ANALYSIS PLAN

This is a Phase I/II, multicenter, open-label, dose-escalation, study designed to evaluate the safety, tolerability, PK, and preliminary efficacy of cobimetinib in pediatric and young adult patients with solid tumors for which prior treatment has proven to be ineffective (i.e., relapsed or refractory) or intolerable. The primary analysis will be conducted after enrollment has been completed and all enrolled patients have been followed for at least 12 months.

6.1 DETERMINATION OF SAMPLE SIZE

For the dose-escalation stage, the sample size is based on the dose-escalation rules described in the study design section of this document. Explicit power and Type I error considerations were not factored into the design, as the dose-escalation stage was designed to obtain preliminary safety and PK information for the study drug.

To make a preliminary assessment of the efficacy of the study drug, two phases of response assessment are planned for the expansion stage: an initial response assessment and an additional response assessment. Taking into account historical control ORRs for each pediatric tumor type, the minimum number of patients in the initial

response assessment and the minimum number of responders needed for advancement to the additional response assessment were calculated and are presented by tumor type in [Table 6](#). The selection of tumor type cohorts for additional response assessment, as well as the number of patients needed for the additional response assessment, will also take into account practical considerations (e.g., enrollment feasibility), biomarker analysis, safety profiles, and any other relevant information. Similar consideration will be given to other rare pediatric tumor types that are enrolled in the study and not included in [Table 6](#). No formal hypothesis testing is planned in this study.

Table 6 Sample Size and Responder Requirements for Initial Response Assessment

Tumor Type (relapsed/refractory)	Historical Control Overall Response Rate (%)	Initial Response Assessment	
		Minimum No. of Patients Enrolled	Minimum No. of Responders Needed for Tumor Type Cohort Expansion
Melanoma	20%	10	3
Neuroblastoma	18%	10	3
Rhabdomyosarcoma	10%	10	2
Non-rhabdomyosarcoma soft tissue sarcoma	10%	10	2
High-grade glioma ^a	12%	10	2
Low-grade glioma ^b	20%	10	3

^a Gururangan et al. 2010; Warren et al. 2012; Fouladi et al. 2013; MacDonald et al. 2013.

^b Packer et al. 2009; Bouffet et al. 2012; Yalon et al. 2013.

Overall, approximately 70 patients will be enrolled in the study.

6.2 SUMMARIES OF CONDUCT OF STUDY

Patient enrollment will be tabulated by study site. Patient disposition and reasons for discontinuations will be summarized for all enrolled patients. In addition, major protocol deviations will be summarized.

Patient demographics and baseline characteristics, including age, sex, race, medical history, and prior cancer treatment, will be summarized overall and by tumor type cohort. Descriptive statistics (mean, median, standard deviation, 25th percentile, 75th percentile, and range) will be presented for continuous variables, and proportions will be presented for categorical variables.

6.3 SAFETY ANALYSES

Safety analyses will be performed on the safety-evaluable population, which is defined as patients who receive any amount of study drug. Subgroup safety analyses by tumor type cohort will also be conducted as appropriate.

Study treatment exposure (such as treatment duration, total dose received, and number of cycles and dose modifications) will be summarized with descriptive statistics.

All adverse events, serious adverse events, adverse events leading to death, DLTs, adverse events of special interest, and adverse events leading to study treatment discontinuation, that occur on or after the first dose of study treatment (i.e., treatment-emergent adverse events), will be summarized by mapped term, appropriate thesaurus level, and toxicity grade. For events of varying severity, the highest grade will be used in the summaries. Deaths and cause of death will be summarized.

Laboratory toxicities will be summarized by NCI CTCAE grade.

6.4 PHARMACOKINETIC ANALYSES

Plasma samples for determination of cobimetinib concentration will be collected prior to dosing and at 2, 4, 6, and 24 hours after dosing on Days 1 and 21 of Cycle 1, and within 4 hours prior to dosing on Day 1 of Cycle 2. The sampling will allow determination of the total exposure (AUC_{0-24} after a single dose and at steady state), C_{max} , T_{max} , and accumulation ratio. Mean and individual concentration-time graphs will be plotted, and PK parameters will be reported using descriptive statistics (e.g., mean, standard deviation, coefficient of variation, median, minimum, and maximum). Other PK parameters such as steady-state concentration, steady-state concentration at the end of a dosing interval, CL/F , and $t_{1/2}$ may be determined as data allow. After a minimum of 20 patients have completed Cycle 1, an interim PK and safety analysis will be conducted.

In addition, cobimetinib plasma concentration-time data, together with information on dosing and patient characteristics, will be pooled and analyzed using a population PK analysis approach.

Additional analyses may be conducted as warranted by the data.

6.5 EFFICACY ANALYSES

All efficacy analyses will be performed on safety-evaluable population, which is defined as patients who receive any amount of study drug.

6.5.1 Primary Efficacy Endpoints

The co-primary endpoints for efficacy are ORR and PFS.

An objective response is defined as a complete or partial response on two consecutive occasions ≥ 4 weeks apart, as determined by the investigator using mINRC for patients with neuroblastoma, RANO criteria for patients with HGG, RANO criteria for patients with LGG, and RECIST v1.1 for patients with other tumors. ORR is the percentage of patients who are determined to have an objective response. Patients with no post-baseline tumor assessments will be counted as non-responders. ORR and

corresponding 95% exact confidence interval (CI), using the Blyth-Still-Casella method, will be summarized overall and by tumor type cohort.

PFS is defined as the time from initiation of study drug to the first documented occurrence of disease progression, as determined by the investigator, or death from any cause, whichever occurs first. Data for patients without disease progression or death will be censored at the date of the last tumor assessment at which the patient was known to be progression-free or, if no tumor assessment is performed after the baseline visit, at the date of initiation of study drug. The Kaplan-Meier approach will be used to estimate median PFS. The 95% CI of the median PFS will be estimated using Brookmeyer and Crowley method. Subgroup analysis of PFS by tumor type cohort will be conducted as appropriate.

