3.4.3 Efficacy Outcome Measures

The co-primary efficacy outcome measures for this study are as follows:

- ORR, defined as the percentage of patients with a complete or partial response for patients with measurable disease or neuroblastoma patients with evaluable disease at baseline, or a complete response for patients with non–measurable but evaluable disease at baseline (except neuroblastoma patients), on two consecutive occasions ≥ 4 weeks apart, as determined by the investigator using mINRC for patients with neuroblastoma (see [Appendix 3](#)), RANO criteria for patients with HGG (see [Appendix 4](#); Wen et al. 2012), for the RANO criteria for patients with LGG (see [Appendix 5](#)) and RECIST v1.1 for patients with other tumors (see [Appendix 6](#)).
- PFS, defined as the time from initiation of study drug to the first documented occurrence of disease progression, as determined by the investigator using mINRC for patients with neuroblastoma (see [Appendix 3](#)), RANO criteria for patients with HGG (see [Appendix 4](#); Wen et al. 2012), RECIST v1.1 for patients with other tumors (see [Appendix 6](#)), and RANO criteria for patients with LGG (see [Appendix 5](#)) in the expansion stage in addition to RECIST v1.1, or death from any cause, whichever occurs first

The secondary efficacy outcome measures for this study are as follows:

- DOR, defined as the time from the first tumor assessment that supports the patient's objective response to the time of disease progression, as determined by the investigator using mINRC for patients with neuroblastoma (see [Appendix 3](#)), RANO criteria for patients with HGG (see [Appendix 4](#); Wen et al. 2012), RECIST v1.1 for patients with other tumors (see [Appendix 6](#)), and RANO criteria for patients with LGG (see [Appendix 5](#)) in the expansion stage in addition to RECIST v1.1, or death from any cause, whichever occurs first
- OS, defined as the time from initiation of study drug to death from any cause

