- VGPR: Greater than 90% decrease of the disease measurement for CT/MRI target lesions, taking as reference the disease measurement done to confirm measurable disease in target lesions at study entry; all preexisting bone lesions with CR by MIBG; MIBG scan can be SD or CR in soft tissue lesions corresponding to lesions on CT/MRI; CR in bone marrow; no new sites of tumor; HVA/VMA normal
- PR: At least a 30% decrease in the disease measurement for CT/MRI target lesions, taking as reference the disease measurement done to confirm measurable disease in target lesions at study entry; bone marrow with CR; MIBG with either PR or CR in bone lesions; MIBG may be SD or CR in soft tissue lesions corresponding to lesions on CT/MRI; HVA/VMA may still be elevated.
- PD: Any one of the following:
 - At least a 20% increase in the disease measurement for CT/MRI target lesions, taking as reference the smallest disease measurement recorded since the start of treatment
 - Appearance of one or more new lesions or new sites of tumor
 - PD as defined above for either bone marrow or MIBG lesions
- SD: Stable disease by either CT/MRI lesion, bone marrow, or MIBG criteria; no new lesions; no new sites of disease

The overall response as assessed at any particular timepoint based on the various disease sites is summarized in the table below.

¹ Brodeur GM, Pritchard J, Berthold F, et al. Revisions of the international criteria for neuroblastoma diagnosis, staging, and response to treatment. *J Clin Oncol* 1993;11:1466–77.

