Appendix 3 International Neuroblastoma Response Criteria (cont.)

Table 1 Overall Response at Any Timepoint

CT/MRI Lesions	MIBG Lesions	Bone Marrow	Catechols	Overall Response
PD	Any	Any	Any	PD
Any	PD	Any	Any	PD
Any	Any	PD	Any	PD
CR	CR	CR	Normal	CR
VGPR	CR in bone lesions ; May have SD/CR in soft tissue sites corresponding to lesions on CT/MRI	CR	Normal	VGPR
PR	PR/CR in bone lesions; May have SD/CR in soft tissue sites corresponding to lesions on CT/MRI	CR	Any	PR
SD	SD	SD	Any	SD
SD/PR/VGPR/CR	SD	SD/CR	Any	SD
SD/PR/VGPR/CR	SD/PR/CR	SD	Any	SD

CR=complete response; CT=computed tomography; MIBG=metaiodobenzylguanidine; MRI=magnetic resonance imaging; PD=progressive disease; PR=partial response; SD=stable disease; VGPR=very good partial response.

Appendix 4

Response Assessment in Neuro-Oncology Criteria for High-Grade Glioma

Response	Criteria
Complete response	
Requires all of the following:
 
 • Complete disappearance of all enhancing measurable and nonmeasurable disease sustained for at least 4 weeks • No new lesions • Stable or improved non-enhancing (T2/FLAIR) lesions • Patients must be off corticosteroids (or on physiological replacement doses only) • Clinical status is stable or improved
Partial response	
Requires all of the following:
 
 • $\geq 50\%$ decrease compared with baseline in the sum of products of perpendicular diameters of all measurable enhancing lesions sustained for at least 4 weeks • No progression of nonmeasurable T1 enhancing disease • No new lesions • Stable or improved non-enhancing (T2/FLAIR) lesions on the same or lower dose of corticosteroids compared to baseline • Clinical status is stable or improved 
Note: Patients with nonmeasurable disease only cannot have a partial response; the best response possible is stable disease

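### The neuroblastoma ORR never says whether VGPR counts, and the Appendix 3 response table scores some scan patterns two ways and others not at all

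*Combined protocol and SAP*

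**What the plan says.** ORR is a co-primary efficacy endpoint. Section 6.5.1 reads: "An objective response is defined as a complete or partial response on two consecutive occasions". Section 3.4.3, matched by the synopsis, has wording specific to neuroblastoma: "the percentage of patients with a complete or partial response for patients with measurable disease or neuroblastoma patients with evaluable disease at baseline". Both name the modified INRC of Appendix 3 as the yardstick for that tumour, and neither mentions VGPR.

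Appendix 3 gives five overall responses: CR, VGPR, PR, SD and PD. Three of its text definitions matter here:

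- VGPR: "VGPR: Greater than 90% decrease of the disease measurement for CT/MRI target lesions", with MIBG bone lesions cleared, marrow CR and normal catecholamines.
- PR: "PR: At least a 30% decrease in the disease measurement for CT/MRI target lesions", with marrow CR, PR or CR of MIBG bone lesions, and catecholamines allowed to stay raised. For soft tissue: "MIBG may be SD or CR in soft tissue lesions corresponding to lesions on CT/MRI".
- SD: "SD: Stable disease by either CT/MRI lesion, bone marrow, or MIBG criteria", with no new disease.

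Table 1 of Appendix 3 turns these into rows. VGPR has its own row and its own output label. For soft tissue, the MIBG cell of the PR row says: "May have SD/CR in soft tissue sites corresponding to lesions on CT/MRI". A later row returns SD for CT/MRI of SD, PR, VGPR or CR when MIBG is SD and marrow is SD or CR.

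Table 6 in Section 6.1 sets the neuroblastoma bar at 3 responders among a minimum of 10 patients, against a historical rate of 18%. Under Section 3.1.2, enrolment in a cohort stops if it has its patients but not its responders.

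**The concern.** The endpoint counts two labels, while the criteria that feed it can return three favourable ones. The omitted label is the better of the two partial grades. Where this protocol wants an extra category counted, it names it: the modified ORR for low-grade glioma in Sections 3.4.4 and 6.6.1 lists minor response explicitly. The neuroblastoma clause in Section 3.4.3 does not do the same for VGPR.

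The response table should give each set of findings exactly one answer. If it gives two, or none, investigators at about 30 sites have to choose, and identical scans can be scored differently. Three results depend on that choice: the reported ORR with its confidence interval, the set of patients in the duration-of-response analysis (Section 6.5.2 restricts it to responders), and the count set against the 3-of-10 bar.

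**Working it through.** **1. Does VGPR count?** By the Appendix 3 text, a VGPR patient meets every element of PR: shrinkage above 90% is also at least 30%; MIBG CR in bone satisfies PR or CR; marrow is CR in both; and normal catecholamines are permitted under PR. By the Table 1 labels the patient is VGPR, because the PR row admits only CT/MRI PR. The text therefore points one way and label-based coding the other, and no sentence decides.

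Confirmation needs two consecutive qualifying assessments at least 4 weeks apart. If VGPR is not a qualifying label:

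- PR, PR, VGPR: already confirmed, no loss.
- PR, VGPR: only one qualifying assessment, not confirmed.
- VGPR, VGPR: none, not confirmed.

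**2. Patterns with two answers.** Take MIBG-avid disease only in soft tissue that matches CT/MRI lesions. If the number of positive lesions is unchanged, Appendix 3 calls MIBG SD. With marrow CR:

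| CT/MRI | MIBG | Marrow | Catecholamines | Table 1 rows met |
|---|---|---|---|---|
| PR | SD | CR | any | PR and SD |
| VGPR | SD | CR | normal | VGPR and SD |

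Table 1 gives no order of precedence. The overlap does not arise with bone-only MIBG disease: there the PR row needs PR or CR in bone, and the SD row that accepts marrow CR needs MIBG SD.

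**3. Patterns with no row that nevertheless meet the PR text.**

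| CT/MRI | MIBG | Marrow | Catecholamines | Table 1 row |
|---|---|---|---|---|
| CR or VGPR | PR in bone | CR | any | none |
| CR | CR | CR | raised | none |
| VGPR | CR | CR | raised | none |

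**4. What a lost responder could do to the count.** Table 6 gives no error rate, power or target rate, so the 3-of-10 figure has no stated operating characteristic to reproduce. For reference, at the historical 18% the chance of 3 or more responders in 10 is 0.26.

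The documents give neither the true response rate p nor the share s of true responders who would go uncounted. Both are assumptions. With q = p(1 − s),

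P(at least 3 of 10) = 1 − (1 − q)^10 − 10q(1 − q)^9 − 45q²(1 − q)^8.

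At q = 0.30 this is 1 − 0.0282 − 0.1211 − 0.2335 = 0.617. The other values are:

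| Share uncounted, s | True rate 30% | True rate 40% |
|---|---|---|
| 0 | 0.62 | 0.83 |
| 10% | 0.53 (q = 0.27) | 0.76 (q = 0.36) |
| 20% | 0.44 (q = 0.24) | 0.67 (q = 0.32) |

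Here s is the share actually uncounted. It is not the share who ever reach VGPR, because step 1 shows that some of those are already confirmed by two earlier PRs.

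**The case against.** The best defence is that VGPR is a partial response by name and by definition. The PR text has no ceiling, so anyone who reads the words rather than the labels will count it. That is probably the intent. A reader might infer that the plan excludes the deepest responders from ORR. The documents do not support that: they leave the matter unsaid, and the open-ended PR text points the other way. What remains is that Table 1 returns a label that the endpoint definition does not list.

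Second, Appendix 3 presents its text criteria as defining overall response and the table as a summary, so a missing row need not lose anyone whom the PR text covers. This weakens the point about empty rows. It does not settle the overlap, because the text has the same clash: PR tolerates unchanged MIBG uptake in soft tissue, while SD is satisfied by stability on MIBG alone. One can argue that the specific allowance should beat the general rule, and that is a sensible reading, but the plan does not state it.

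Third, the overlap is narrow. It needs soft-tissue-only MIBG disease with an unchanged lesion count, and the documents do not say how often that occurs.

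Fourth, a reader might infer that an active cohort would be stopped. Sections 3.1.2 and 6.1 make that far from automatic. Further enrolment may be approved before the initial assessment, a slow-enrolling rare cohort with a strong signal may be extended, other information is weighed, ten is a minimum, and no formal test is planned. A neuroblastoma cohort might also not be among those chosen. This discretion softens the go decision. It does not define the ORR that will be reported.

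**Conclusion.** The point holds as an ambiguity and an internal contradiction in how a co-primary endpoint is scored for one tumour type. The endpoint wording does not settle VGPR; Table 1 gives conflicting results for two patterns and none for several that meet the PR text. A responder could therefore be lost from ORR, from duration of response and from the 3-of-10 count.

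The documents do not allow the size of any loss to be derived. If one true responder in ten went uncounted, the chance of meeting the bar would drop by about 8 percentage points at a true rate of 30% and about 7 at 40%. Those figures rest on assumed rates and an assumed loss, and they ignore the sponsor's discretion. A larger drop, obtained by treating every patient who reaches VGPR as lost, is not supported.

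**What to change.** 1. In the synopsis, Section 3.4.3 and Section 6.5.1, define objective response for neuroblastoma as an overall CR, VGPR or PR under Appendix 3, confirmed by any two consecutive of these at least 4 weeks apart.
2. In Appendix 3 Table 1, state that MIBG SD confined to soft tissue matching a CT/MRI lesion does not trigger the SD row when the PR or VGPR row is otherwise met.
3. In the same table, widen the CT/MRI cell of the PR row to PR, VGPR or CR, for patients who do not meet the CR or VGPR row.
4. Confirm that the 18% historical rate, for which Table 6 cites no source, uses the same response definition, since the bar of 3 was set against it.

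The cost is one sentence in three places, two edits to a table and one check of a source. No new data, patients or assessments are needed.
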